Just as telemedicine has expanded the scope of clinical care, it is also expanding the scope of clinical trials²³. The outpatient psychiatry clinics at Massachusetts General Hospital have used telemedicine for routine clinic appointments for qualifying patients after an in-person consultation. Telemedicine significantly lessens patient burden, as the patient does not have to come into the office for appointments, but still receives the same level of clinical care through the face-to-face video conference. Our research unit has conducted telemedicine research with positive experiences. As such, we propose to offer the option of telemedicine visits in this study.

II. SPECIFIC AIMS

Aim 1: Assess effect of solriamfetol on ADHD symptoms and associated ADHD features.

Hypothesis 1: Compared to pre-administration baseline, solriamfetol will be associated with a greater reduction than placebo of ADHD symptoms (1a). We also expect drug exposure to be correlated with a greater rate of individuals achieving an a priori definition of clinical improvement, with at least a 25% reduction in ADHD symptoms, and a CGI of much or very much improved (1b).

We secondarily will explore whether there are reduced symptoms of executive dysfunction (defined by a 0.5 standard deviation improvement on the Brief Rating Inventory of Executive Function-Adult Version (BRIEF-A) self-report total or subscale scores). We also will explore whether baseline ratings of sleepiness, or deficits on BRIEF predict improvements on the Adult ADHD Investigator Symptom Rating Scale (AISRS) or BRIEF measures.

Aim 2: Assess the safety of solriamfetol in the treatment of ADHD among adults

Hypothesis 2: Solriamfetol will be well tolerated by adults with ADHD.

III. SUBJECT SELECTION

We plan to enroll 60 subjects of any gender identity between the ages of 18-65 in the study. No pediatric subjects will be recruited for this study. We will recruit subjects through advertisement in the general community, using flyer and internet advertisements, via postings on Rally, Research Match, and from the referral pool of patients of the Clinical and Research Program in Pediatric Psychopharmacology and Adult ADHD at Massachusetts General Hospital. As noted elsewhere, however, the informed consent process with a subject must occur with a different clinician than one they have seen as a treating provider.

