We anticipate that a small minority of subjects may enter this trial following completion of withdrawal from other protocols in our office, and that there may be procedural overlap. So as to not burden subjects with redundant time commitments, we will use the following *diagnostic* data previously collected: If a subject has completed an equivalent evaluation with one of the study clinicians within the previous year prior to entrance into this study, they will not be asked to repeat any overlapping diagnostic procedures. With subjects' permission, we will use the diagnostic data that had been previously collected, and document this data and when it was collected in our substantiation of how the individual meets diagnostic criteria in the evaluation documentation for the current study. However, the study clinician will review the interval time period to assess for clinically significant medical or psychiatric history, to ensure that the subject meets all study entrance criteria.

Safety Assessments:

Vital signs (blood pressure, pulse) will be monitored at each visit during the study. If there is suspicion that the participant's eligibility to participate has changed (e.g., evidence they have taken an illicit drug), he/she will have a discussion with the doctor to determine if he/she can be in the study. It will be up to the principal investigator's judgement to determine if the subject continues to meet study inclusion and exclusion criteria. For example, subjects will be discontinued if there is suspicion of ongoing substance abuse by history or by confirmation of ongoing abuse by positive drug test, or evidence of inability to adhere to study procedures (e.g. missing two visits in a row, or otherwise insufficient participation to monitor safety in the judgement of the investigators). Drug testing will not

be done systematically but will be available to clinical investigators to determine participant eligibility and safety before and throughout study participation. Participants will be told at the time of consent that random drug screening may occur at the choice of study investigators.

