Randomization to active or placebo will occur once a subject is scheduled for a baseline visit, when the clinical trials pharmacy will be given a subject name that the pharmacy will associate with a number identifier. We have extensive experience maintaining blinding, wherein we have our central Mass General Hospital Clinical Trials Pharmacy pharmacy serve as the only part of the greater trial team that is aware of the assignment to active or placebo during study participation. The trials pharmacy will receive products identified by the sponsor as active or placebo fill, over-encapsulate these products to look identical, bottle these products with unique identifiers, maintains the placeboactive ratio, and maintain blinding until study completion. For the purpose of the final analysis, the official clinical database will not be unblinded until medical/scientific review has been completed, protocol violators have been identified (if appropriate), and data collection has been declared complete. In the extreme event where subject safety will be compromised by maintaining the blind, eg. an adverse event where treatment is dependent on knowing if they were on active or placebo medication, we will unblind the status of the subject's study agent, following emergency protocols in place in our department and institution.

Assessments and Instruments:

Our primary endpoint will be change in the Adult ADHD Investigator Symptom Rating Scale (AISRS), the instrument we will use to evaluate ADHD symptom burden. We also will evaluate spontaneously reported adverse events as our main outcome of tolerability. At screening evaluation, AISRS ratings and concurrent medication treatments will be recorded. In addition, at screening or baseline, a brief demographic interview will be conducted to obtain information used to calculate socioeconomic status.

Demographic information, including socioeconomic status data, will collected for each participant.²⁴

During the study, the following assessments and instruments will be used:

Clinician rated assessments (rated at each in-office study visit, unless otherwise noted):

- Global Assessment of Functioning (GAF) scale. The GAF will assess global functioning using a scale from 1 (worst) to 100 (best). This will be collected at all study visits, excluding the screening visit.
- Clinical Global Impressions (CGI) scale for ADHD. The CGI is a measure of illness severity, improvement, and efficacy of treatment.

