Examples of individuals who will discontinue study participation include those who: 1) develop intolerable adverse events (AEs) despite dose adjustments; 2) have (a) clinically relevant serious AE(s) as determined by the investigator; 3) have worsening ADHD symptoms (much worse or very much worse as rated on CGI-Improvement at two consecutive visits); or 4) have emergent adverse mental health state including psychosis, suicidality, substance use, or worsening mood and/or anxiety; 5) are non-adherent to study procedures or withdraw from the study; 6) intend to be or become pregnant.

If study participation is discontinued due to safety reasons, participants will receive two followup visits, giving adequate time for appropriate psychiatric referrals to treaters in their communities. Subjects found to be taking substances listed as exclusionary during the course of the study may be discontinued based on PI evaluation of their eligibility.

VI. BIOSTATISTICAL ANALYSIS

Data processing and management followed procedures developed by the investigators and used in ongoing studies. Up to 30 subjects will receive Solriamfetol, and up to 30 subjects will receive placebo. Changes in outcome ratings within and between study groups will be tested.

Hypothesis 1 will be our main testable hypothesis, tested by evaluating whether the group receiving stimulant treatment has a significantly greater improvement in ADHD symptom rating. We will also explore exploratory hypotheses. This will include comparing the active and placebo arms on: the rate of individuals achieving an a priori definition of clinical improvement, with at least a 25% reduction in ADHD symptoms, and a CGI of much or very much improved (1b), and the rate of reduced symptoms of executive dysfunction (defined by a 0.5 standard deviation improvement on BRIEF-A self-report total or subscale scores) (1c).

All other analyses will be exploratory and p-values will be reported as nominal, and not used to infer significance. We will also explore descriptively whether baseline sleep problems, sleepiness, or deficits in domains of the BRIEF predict improvement on AISRS or BRIEF ratings.

Our primary test of Hypothesis 2 will be review of the occurrence of moderate or severe adverse events, and description of reasons for study dropout. We will also report rates of the same adverse event in active and placebo arms occurring two or more times for a particular subject.

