We will also report whether there is a difference in change in baseline to endpoint sleepiness and changes in sleep quality during the study.

Data processing and management will follow procedures developed by the investigators and used in ongoing studies.

VII. RISKS AND DISCOMFORTS

All efforts are made to minimize risks to subjects. Consistent with good clinical practice, safety will be monitored by the Principal Investigator, and will reflect the oversight of co-investigator study clinicians. Adverse events will be recorded and reported according to institutional policies. Risks of the study agent have been considered in developing the exclusionary criteria for this proposal.

Study clinician evaluation and subject questionnaires:

Some questions may make subjects feel uncomfortable. Subjects may refuse to answer any question they wish. In the event that a participant reports risk of harm to himself or herself, or to another person, study clinicians will assess the level of risk, and take appropriate actions, including disposition of an immediate referral to a local Psychiatric Emergency Room.

Risks of Study Agent – Solriamfetol:

Solriamfetol is approved by the US Food and Drug Administration to improve wakefulness in adult patients with excessive daytime sleepiness associated with narcolepsy or obstructive sleep apnea (OSA).

FDA indications for Solriamfetol include recommendation for starting at 75 mg in patients with daytime fatigue in narcolepsy, and titration from 75 mg to 150 mg after three days. Our protocol titrates more conservatively, following the weekly pattern of dose increase that is more typical of clinical trials in ADHD. While this interval for increase was chosen primarily to give subjects longer to evaluate ADHD symptom experiences, and to mimic pattern of study assessments in other ADHD trials, it will also give greater time for subjects to evaluate adverse effects before increasing them with a dose increase.

We chose not to exceed 150 mg in this study in keeping with FDA approved dosing for individuals with excessive daytime sleepiness. The package label notes that heart rate and blood pressure changes appear to be dose-dependent in populations studied, such that doses above 150 mg could be expected to add more risk. The label advises to avoid patients with known cardiovascular and cerebrovascular disease, preexisting hypertension, and patients with advanced age, advice we follow in this protocol.

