Vital Signs (BP, pulse)		X*	х	х	х	х	х	x
Clinician Evaluation	x							
AISRS	х	х	х	х	х	х	х	х
ADHD-RS	X*							х
CGI ratings		х	х	х	х	х	х	х
GAF		х	х	х	х	х	х	х
Adverse Events		x	х	х	х	x	x	х
Concomitant Medications		х	х	х	х	х	х	x
BRIEF-A		X*						х
ASR	X*							
ESS		X*						х
PSQI		X*						х
Pill counting				х		х		х
Pregnancy test	х							х

^{*} Can be completed at either evaluation or baseline visit as long as those visits are within 10 days

^{**}If a subject terminates participation early, all assessments at week 6 will be made at study completion.

IX. Monitoring and Quality Assurance

The Principal Investigator will meet regularly with study staff to address procedural issues and the study coordinator will audit each subject's data within 48 hours of each study visit. Furthermore, all data will be audited by the study statistician with the assistance of the database manager on a regular basis to ensure the progress of the study and confirm that all necessary data is being collected and can be transitioned to the statistical package smoothly. Co-investigators are actively involved in the monitoring and quality assurance of these trials. Periodic quality assurance audits will ensure accuracy and completeness of all subject documents, IRB files and correspondence, and the informed consent documentation.

XI. Telehealth Remote study procedures

Subjects will be offered the option to participate via remote telehealth. Individuals may choose a mixture of in-person and telehealth visits, or just one or the other, as suits scheduling convenience or prudent safety practice. For example, during a public health infectious disease crisis such as the COVID-19 pandemic, risks to participants may be reduced by remote televisits. We will not conduct in-person visits unless approved by Partners healthcare and Massachusetts General Hospital.

Recent Virtual Visit Clinical Growth for COVID-19

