Women of child-bearing potential will complete a urine pregnancy test as part of the evaluation study visit and Week 6/drop study visits. Study staff will order a urine pregnancy test online and ship it directly to the participant's home address. The test will be ordered and shipped in advance to ensure delivery prior to the applicable study visit. On the day of the visit, the participant will complete the test after the study coordinator or a study clinician has reviewed the proper procedure for completing the test. In addition, the participant will provide the study coordinator with visual confirmation of the result via TeleHealth video system or image sent by (un)encrypted email.

Vital Signs

The study coordinator will ship a blood pressure and heart rate monitor to each participant, and ask the participant to self-report the vital signs on the same day as the study visit via telephone call or image sent by (un)encrypted email. The study coordinator will note that these data points were provided by study subject report, rather than study staff measurement.

III. Remote Study Medication Dispensation

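### Blood pressure and pulse are collected through week 6, but the Hypothesis 2 analysis plans no comparison of them between arms

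*Combined protocol and SAP*

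**What the plan says.** **Collection.** Section V, Safety Assessments: "Vital signs (blood pressure, pulse) will be monitored at each visit during the study". The Visual Timeline has a row for vital signs marked at baseline and at weeks 1 to 6, the last column being week 6 or the drop visit. A footnote lets the baseline reading be taken at the evaluation visit if the two visits fall within 10 days. For remote visits, the Vital Signs paragraph of the telehealth section says that the coordinator will ship a monitor and "ask the participant to self-report the vital signs on the same day as the study visit". The coordinator notes that such readings were reported by the participant.

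**Stated risk.** Section VII, Risks of Study Agent: "The package label notes that heart rate and blood pressure changes appear to be dose-dependent in populations studied". The sentence goes on to explain why the trial does not go above 150 mg. The same section repeats label advice to measure heart rate and blood pressure before and during treatment.

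**Safety hypothesis and outcome.** Section II, Hypothesis 2: "Solriamfetol will be well tolerated by adults with ADHD". No numerical criterion is attached. Section V, Assessments and Instruments: "We also will evaluate spontaneously reported adverse events as our main outcome of tolerability".

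**Analysis.** Section VI: "Our primary test of Hypothesis 2 will be review of the occurrence of moderate or severe adverse events". It also plans a description of dropout reasons and by-arm rates of the same event occurring at least twice in a subject. It separately plans to report changes in sleepiness and sleep quality. Blood pressure and pulse are not mentioned in Section VI.

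**The concern.** The trial takes repeated, placebo-controlled readings of two quantities that its own risk section links to dose, but its analysis plan does not use them. The Hypothesis 2 analysis works through events: what a participant reports, how severe the investigator grades it, and why someone leaves. A modest upward shift across the active arm need not produce a moderate or severe event in any one person. Monitoring individuals under the blind cannot show a difference between arms either.

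At stake is the support for the Aim 2 conclusion. Section I says that the drug has not been evaluated in ADHD and that the study is meant to assess safety as well as efficacy. Followed exactly, Section VI would allow a favourable tolerability statement with no by-arm estimate of blood pressure or pulse. A table could be added later, but the measures, visits and cut-offs shown would then be chosen after the data are unblinded.

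**Working it through.** **Step 1: does any planned analysis cover vital signs?** The candidates in Section VI, one by one:

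- *Moderate or severe adverse events.* Covers a vital-sign change only if someone records it as an event of that severity.
- *Reasons for dropout.* The examples under Study Discontinuation Criteria name no blood pressure or pulse item. A case could arise under intolerable or serious events, but only case by case.
- *Same event at least twice in a subject.* Again requires a recorded event.
- *The general sentence on testing changes in outcome ratings within and between groups.* Blood pressure and pulse are measurements, not ratings, and are not named.
- *Changes in sleepiness and sleep quality.* These rated measures get their own sentence; vital signs get none.

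No by-arm summary, comparison or threshold count of blood pressure or pulse is planned.

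**Step 2: is there a figure of the plan's own to reproduce?** No. The documents give no SD, significance level, power, dropout rate or sample-size calculation.

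**Step 3: what could the collected data deliver?**

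Inputs: n = 30 per arm, the maximum in Section VI. The SD of change from baseline, s, is an assumption: 6 to 12 units (mmHg or beats per minute).

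95% half-width for the arm difference in change at one visit = t(0.975, 2n − 2) × s × √(2/n).

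With n = 30, t(0.975, 58) = 2.002 and √(2/30) = 0.2582. Difference detectable with 80% power at two-sided 5% = (1.960 + 0.842) × s × 0.2582.

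| Assumed SD of change | 95% half-width | Detectable difference |
|---|---|---|
| 6 | 2.002 × 6 × 0.2582 = 3.1 | 4.3 |
| 8 | 4.1 | 5.8 |
| 10 | 5.2 | 7.2 |
| 12 | 6.2 | 8.7 |

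At an assumed 25 per arm with data, t(0.975, 48) = 2.011 and √(2/25) = 0.2828. The half-width then runs from 3.4 (SD 6) to 6.8 (SD 12).

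**Step 4: effect of baseline adjustment.** If the SD is equal at the two times and the within-person correlation is r, the variance of a change score is proportional to 2(1 − r) and that of a baseline-adjusted value to 1 − r². Their ratio, adjusted to change, is (1 + r)/2, which cannot exceed 1. Apart from small-sample loss, the adjusted estimate is therefore no less precise than the figures in the table.

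These figures describe the precision of the proposed analysis. They do not measure any drug effect or the probability that a signal would be missed.

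**The case against.** The strongest reply is that cardiovascular safety is not ignored. Vital signs are watched throughout, the Principal Investigator oversees safety, and every adverse event is graded for severity and relatedness. The section on adverse event reporting counts an abnormal sign as a possible adverse event, so a notable pressure or pulse abnormality can reach the planned review. This stands. A reader might infer that tolerability would be judged with no cardiovascular information at all; the documents do not support that. Nor do they contain any figure on how often such rises surface as reported events, so a claim that they rarely do would have no source here. What remains is a shift between arms that nobody records as a moderate or severe event.

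Second, the sentence on dose-dependence justifies the 150 mg ceiling. It does not rank these changes as the leading hazard, and the common reactions listed in Section VII are headache, nausea, decreased appetite, insomnia and anxiety. This also stands. The sentence and the repeated label advice show that the measure is relevant, not that it is the main safety question.

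Third, this is a 60-person pilot with otherwise exploratory analyses, so an elaborate model or a borrowed threshold would be out of proportion. This is accepted. Averaging weeks 1 to 6 would mix readings taken at 75 mg with later ones at 150 mg or after a return to 75 mg. The 140/90 figure in the exclusion criteria is an entry criterion and need not serve as an on-treatment cut-off. Neither is needed to close the gap.

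**Conclusion.** The point holds in a limited form. Blood pressure and pulse are collected at baseline and weeks 1 to 6, the protocol notes that they change with dose, and Section VI plans no by-arm comparison of them. A between-arm shift that does not appear as a moderate or severe adverse event could go unseen when Hypothesis 2 is judged.

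The missing analysis is feasible. With 30 per arm and an assumed SD of change of 6 to 12 units, a one-visit comparison would carry a 95% half-width of about 3 to 6 units. Fewer participants with data would widen it, and participant-reported readings make the assumed SD less certain. That is enough for a useful estimate but not to exclude small mean shifts, so it should not be presented as a powered test.

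The gap does not invalidate the trial. It should be closed because the data will exist anyway and the safety conclusion is weaker without them.

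**What to change.** Add to the Hypothesis 2 paragraph of Section VI, labelled as exploratory estimation:

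1. The between-arm difference in systolic pressure, diastolic pressure and pulse, adjusted for baseline, at each visit from week 1 and at week 6/drop, with 95% confidence intervals. Reporting by visit keeps the titration weeks separate.
2. By-arm counts of readings above a descriptive reporting cut-off. The investigators choose it and record it before unblinding; it is for tabulation only and changes no clinical rule.
3. A flag for self-reported versus staff-measured readings, using the note that the coordinator already makes.
4. The number of participants contributing at each visit, so that the effect of dropout on precision is visible.

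The cost is a few lines in Section VI and one extra table. No new data, visits or procedures are needed.

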Females who are able to have children will also have a urine pregnancy test at evaluation, and week 6 or study completion. If a participant has a positive pregnancy test she will not be able to take part in the study. As detailed in the exclusion criteria, all participants will be required to use contraception adequate to avoid conception, or to not participate. In the event that a subject becomes pregnant, we will ask the subject's permission to obtain information about the outcome of the pregnancy and the condition of the newborn. In the event that a subject reports contributing sperm to a pregnancy during the study period, we will also ask the subject's permission to obtain information about the outcome of the pregnancy and the condition of the newborn. Those subjects who terminate study participation before the completion of the study will be asked to complete all tasks scheduled to take place on the final study visit at the time of study discontinuation.

We will increase our chances of identifying exclusionary mental health conditions by supplementing the clinical interview for study eligibility with review of self-report on the Adult Self-Report (ASR), a self-report scale validated to identify major mental health conditions, prior to participation.

Subject Dosing and Visit schedule:

Visits will occur for evaluation, baseline, and weekly for weeks 1, 2, 3, 4, 5 and 6. Visits will be conducted at 7 day intervals, +/- 3 days. Doses will be assigned at each study visit for the period of time until the next visit, with forced-dose up-titration as tolerated from 75 mg at week one to 150 mg at week 2, and with intention that dosing remain stable for the last four weeks of study participation, such that investigators will ask a subject to go back down to 75 mg during any of the weeks following week 2 only if only if 150 mg is not tolerated. Thus, the most robust titration would be 75 mg until week 1, and 150 mg for the rest of study. The least robust titration where a subject maintains participation would be 75 mg for the duration of the study.

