- Adult ADHD Investigator Symptom Rating Scale (AISRS). Each of the individual symptoms of ADHD is rated 0 to 3 on a scale of severity.
- Adverse Experiences (collected at all visits excluding the screening and baseline visits) and Concomitant Medications.

Subject rated scales (all scales rated at baseline and week 6 or drop visit:

- The 18-item ADHD Rating Scale to evaluate frequency of ADHD symptoms on a scale of 0 to 4 (ADHD-RS).
- The 86-item Behavior Rating Inventory of Executive Function Adult Form (BRIEF-A) to assess levels of executive function deficits.
- Pittsburgh Sleep Quality Index. This Index is a widely used measure which consists of 19 items which assess sleep quality over one month time period.
- Epworth Sleepiness Scale

Subject rated scale at baseline only

 In addition, at baseline the The Adult Self-Report Form (ASR) to measure a wide range of psychiatric syndromes (i.e., depressive problems, anxiety problems, antisocial personality problems) in adults. The ASR provides dimensional scale scores for each syndrome that are age- and gender-normed. ²⁶

Adverse Event Assessment and Reporting

All solriamfetol treatment-emergent serious adverse events (initial and follow-up) that require collection per protocol will be reported to Axsome Therapeutics via email within 1 business day of awareness of the serious adverse event.

As noted above, adverse events will be recorded at all visits other than screening and baseline. Investigators will characterize adverse event by description, note the severity (mild, moderate, or severe), whether it is expected (yes or no), relatedness (unrelated, definite, probable, or possible).

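### The primary test of Hypothesis 2 leaves out failure to reach or stay on 150 mg, and no planned analysis reports it by arm

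*Combined protocol and SAP*

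**What the plan says.** Hypothesis 2 (Section II) reads: "Solriamfetol will be well tolerated by adults with ADHD". It sets no threshold and names no dose.

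Section VI gives the analysis: the primary test of Hypothesis 2 is "review of the occurrence of moderate or severe adverse events, and description of reasons for study dropout". The next sentence adds a second report, by arm and without a severity limit: "We will also report rates of the same adverse event in active and placebo arms occurring two or more times for a particular subject". Section V (Assessments and Instruments) takes a broader view of the outcome: "We also will evaluate spontaneously reported adverse events as our main outcome of tolerability".

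The dosing rules are in Section V (Subject Dosing and Visit schedule). Titration from 75 mg to 150 mg is forced, subject to tolerability. After that, "investigators will ask a subject to go back down to 75 mg during any of the weeks following week 2" only where 150 mg is not tolerated. Staying low does not end participation: "The least robust titration where a subject maintains participation would be 75 mg for the duration of the study". The Study Discontinuation Criteria remove a participant for intolerable events only when dose adjustment has not resolved them.

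For each adverse event, investigators describe it and "note the severity (mild, moderate, or severe), whether it is expected (yes or no), relatedness". Action taken on dose is not among the listed attributes. Dose is set at each visit, but it is not a row in the timeline table and does not appear in any analysis in Section VI.

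**The concern.** Under this protocol, lowering the dose is the first response to intolerance, and dropout comes only if that fails. A return to 75 mg is therefore the trial's own marker that 150 mg was not tolerated. The primary test of Hypothesis 2 looks at event severity and at dropout, and the step-down falls between the two. A participant whose limiting event was graded mild, and who carried on at 75 mg, contributes to neither component.

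What is at stake is how complete the tolerability conclusion is. The trial could report few moderate or severe events and few dropouts while a noticeable share of the active arm could not take 150 mg, and the planned outputs would not show it. For a pilot meant to inform later work, the proportion reaching and keeping the upper dose is basic information.

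**Working it through.** **No figure to reproduce.** The documents give no step-down rate, adverse event rate or dropout rate, and no calculation for Hypothesis 2. The check is a reading of where each type of participant would be counted, followed by an illustration on assumed rates.

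**Where a participant who cannot take 150 mg is counted**

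| Course | Moderate/severe event component | Dropout component | Recurrent-event report | Dose change recorded in any analysis |
|---|---|---|---|---|
| Limiting event moderate or severe, continues on 75 mg | Yes, as an event | No | If the event recurs | No |
| Limiting event mild, continues on 75 mg | No | No | If the event recurs | No |
| Leaves the trial despite dose adjustment | If so graded | Yes | If the event recurs | No |

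The second row is missed by both primary components. The last column is empty throughout.

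**How many could be missed**

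Inputs: n = 30 in the active arm (Section VI, stated as a maximum); s = share never raised to, or returned from, 150 mg (assumed, 10% to 40%); m = share of those whose limiting event is graded mild, who stay in the trial and have no other moderate or severe event (assumed, 25% to 75%).

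Expected number in neither component = n × s × m.

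| s | m = 25% | m = 50% | m = 75% |
|---|---|---|---|
| 10% | 0.75 | 1.5 | 2.25 |
| 20% | 1.5 | 3.0 | 4.5 |
| 30% | 2.25 | 4.5 | 6.75 |
| 40% | 3.0 | 6.0 | 9.0 |

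For example, 30 × 0.20 × 0.50 = 3. The range is about 1 to 9 of 30.

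**What the added summary could show at this size**

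Exact (Clopper-Pearson) 95% intervals for x of 30, with limits the 2.5% point of Beta(x, 31 − x) and the 97.5% point of Beta(x + 1, 30 − x):

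- 0/30: 0% (0 to 11.6%)
- 3/30: 10% (2.1 to 26.5%)
- 6/30: 20% (7.7 to 38.6%)
- 9/30: 30% (14.7 to 49.4%)
- 12/30: 40% (22.7 to 59.4%)

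For a between-arm difference of 30% versus 10% (assumed), the standard error is √(0.30 × 0.70/30 + 0.10 × 0.90/30) = √0.010 = 0.10. The approximate 95% interval is 20 ± 19.6 points, or 0.4 to 39.6.

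Power of a two-sided Fisher exact test at 0.05 with 30 per arm, on assumed rates: 24% for 20% versus 5%, 37% for 30% versus 10%, 63% for 30% versus 5%, and 89% for 40% versus 5%. The outcome is suited to estimation, not to a confirmatory test.

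**The case against.** The other side has a substantial case.

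- **Mild events are not ignored.** A reader might infer that the tolerability assessment sees only moderate or severe events and dropouts, so that dose intolerance can never surface. The documents do not support that. Section VI also reports recurrent events by arm at any severity, and Section V makes spontaneously reported events, without a grade limit, the main tolerability outcome. A mild event behind a step-down may appear in either. This stands, and it confines the point to the primary test and to the dose change itself.
- **Silence is not a plan to omit.** Nothing in Section VI forbids reporting final dose or separating events by dose. Dose is fixed between visits and events are collected weekly after baseline, so the dose around an event can largely be derived. This stands: new event-record fields are not needed.
- **An extreme illustration would overstate the effect.** If every step-down were assumed to follow a mild event, the primary test would show nothing however many participants stepped down. The documents do not define the grades, and nothing supports that assumption. This stands, and is why a range is used above.
- **Staying on 75 mg does not refute Hypothesis 2.** The hypothesis concerns solriamfetol, not 150 mg, and 75 mg throughout is a permitted course. This stands. It does not make the proportion held at 75 mg uninformative about tolerability.
- **No decision rule is distorted.** Hypothesis 2 is descriptive, in a pilot, with no threshold. This also stands: no error rate is affected.

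None of these brings the dose outcome into a planned analysis.

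**Conclusion.** The point holds in a limited form. The primary test of Hypothesis 2 can miss participants who could not take 150 mg because of mild events and who stayed in the trial, and no planned analysis in any section summarises dose reached or dose reduction by arm. On the assumed rates above, about 1 to 9 of up to 30 active participants would fall outside both primary components. The documents supply neither rate, so this is a range of possibilities and not an estimate.

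The consequence is an incomplete description of tolerability. It would go too far to say that the trial cannot detect intolerance, or that a favourable conclusion would be wrong. It is a worthwhile and inexpensive improvement, not a flaw that invalidates Hypothesis 2.

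**What to change.** In Section VI, add to the Hypothesis 2 assessment one table by randomised arm, with all randomised and dosed participants as the denominator:

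- number and percent never raised to 150 mg, with reason, so that those who left before the increase was due can be told apart from those held for tolerability;
- number and percent returned to 75 mg, with week, reason and severity of the triggering event;
- dose at the last visit.

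Give each proportion an exact 95% confidence interval and report the between-arm difference, labelled as descriptive and not as a confirmatory test. The placebo arm is a valid blinded comparator, because both arms take one or two 75 mg capsules made to look identical, so the same nominal steps exist under placebo.

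I would not tabulate events by dose at onset against placebo participants on the same nominal step. Those groups are selected after randomisation. Later time on 75 mg would belong mostly to people who did not tolerate two capsules, so dose would be confounded with time and intolerance.

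Cost: one extra table from dose assignments already made at each visit, with the reason for any reduction noted. There are no extra visits or participants and no change to dosing. The drawback is wide intervals at 30 per arm, as shown above.
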